Academic and Community Cancer Research United (ACCRU)

ACCRU-GI-1611 COLOMATE: COlorectal Cancer Liquid BiOpsy Screening Protocol for Molecularly Assigned ThErapy

Amendment 2– January 28, 2021

Summary of Changes			
Protocol section updated Nature of change			
Title Page	 Stat personnel change – [name] Updated Document History 		
Section 3.0, Patient Eligibility	• Section 3.19 updated to clarify that one of two conditions must be met		
Section 4.0, Test Schedule	 28 days prior to registration changed to 60 days prio to registration Tumor assessment test removed Footnote 1 Removed Footnotes renumbered 		
Section 6.0, Registration/Randomization Procedures	• Added Exemption: Guardant360 tests completed ≤60 days prior to registration will be accepted		
Section 14.0, Body Fluid Biospecimens	• Instructional text updated throughout for ordering Guardant 360 kits		
Section 16.0, Statistical Considerations and Methodology	 Edit of primary endpoint for actionable genomic profile and trial recommendations Edit of secondary endpoint for companion trial enrollment Addition of confidence interval table in sample size section Analysis plan edit for primary endpoint, goal of 20% of patients with actionable genomic profiles. Addition of secondary endpoint analysis, subsequent screening, goal of 75% patients with actionable genomic profiles. 		
Appendix I: ACCRU Informed Consent	 Removed the need for CT or MRI of tumor Added information regarding the protocol selection process based off of the Guardant360 blood test 		

[figure not shown]
A replacement protocol is provided. Please replace the current copy with the one attached.

Please keep this summary of changes with your protocol

Academic and Community Cancer Research United (ACCRU)

COLOMATE: COlorectal Cancer Liquid BiOpsy Screening Protocol for Molecularly Assigned ThErapy

For any communications regarding this protocol, please contact the person indicated on the Protocol Resource Page. This is a stand-alone document found on the ACCRU website

 $\sqrt{\text{Study contributor(s)}}$ not responsible for patient care.

Research Coordinating Center

Academic and Community Cancer Research United

Document History	(effective date)	
Version 1	May 15, 2017	
Preactivation Amendment	November 8, 2018	
Activation	November 1, 2019	
Amendment 1	March 4, 2020	
Amendment 2	January 28, 2021	

[figure not shown]
Index

0				

Appendix I ACCRU Informed Consent Template

Schema

Patients have the option to register on COLOMATE for a maximum of 3 times or at the discretion of the Study Chair. Reference section 6.2 for instructions.

1.0 Background

Colorectal cancer (CRC) is the second leading cause of cancer death in the United States (Jemal, Siegel et al. 2010). Over the past two decades, overall survival for patients with metastatic disease has steadily improved. To build on this progress, comprehensive efforts are needed to identify and treat actionable molecular alterations. Already, this approach has been used to enhance the benefit of anti-EGFR (Oliner, Douillard et al. 2013) and anti-PD-1 (Le, Uram et al. 2015) monoclonal antibodies. This screening protocol is designed to identify actionable genomic alterations, and then facilitate accrual to molecularly assigned therapies.

Several basket trials are ongoing to match tumor genotype with targeted therapies. Nonetheless, the impact of these trials thus far has been limited by operational and technical challenges. For example, at MD Anderson Cancer Center large-scale genomic testing was performed on 2,000 consecutive patients. Of these, 39% of patients had a potentially actionable tumor mutation, but only 11% were enrolled on a genotype-matched clinical trial (Meric-Bernstam, Brusco et al. 2015). This experience identified several barriers to trial enrollment, including use of non-investigational treatments off trial, excessive delays in receiving test results, declining performance status, and lack of available tumor tissue for testing. To capture the value of mutational testing, it is critical to have an efficient screening process, provide convenient access to clinical trials, and offer treatments with a high probability of clinical benefit.

1.1 Study Rationale

Precision medicine is predicated on the notion that therapeutic strategies can be tailored to a tumor's unique molecular profile. Nonetheless, in practice most targeted therapeutic strategies provide limited clinical benefit. There are several reasons that many targeted therapies fail to provide durable disease control. First, tumor heterogeneity allows rapid outgrowth of resistant subclones (Gerlinger, Rowan et al. 2012). Second, molecular targets that are actionable in one tumor type may not be actionable in another tumor type (Kopetz, Desai et al. 2015). Finally, targeted therapies may induce feedback re-activation of upstream receptors and alternate signaling pathways (Corcoran, Ebi et al. 2012, Mao, Tian et al. 2013). To understand the drivers of sensitivity and resistance, it is critical to understand a tumor's molecular profile before therapy, during therapy, and at progression.

Access to tumor tissue hinders the ability to understand and treat the molecular drivers of resistance. In recent years, technology has emerged to identify genomic alterations from a routine blood draw. In a series of simultaneously obtained blood and tissue biopsies, concordance between circulating cell free tumor DNA (cfDNA) and tissue mutation profiles approached 90% (Kim, Lee et al. 2015, Janku, Huang et al. 2016, Sacher,

Paweletz et al. 2016). For patients with treatment refractory disease, sampling cfDNA for genomic alterations may be particularly valuable. A peripheral blood draw spares a patient an invasive tissue biopsy, and offers rapid, safe, and cost-effective genomic profiling. In addition, blood-based biopsies offer anatomically unbiased genomic profiling, allowing detection of both dominant clones and resistant sub-clones.

The use of cfDNA in treatment-refractory metastatic CRC is feasible, with tumor DNA detected in most patients (Bettegowda, Sausen et al. 2014). Among patients who have progressed on anti-EGFR therapy, cfDNA is already being used to identify molecular drivers of resistance. Some of these drivers, such as ERBB2 amplification, are often present in original diagnostic tumor tissue, and likely represent a primary driver of EGFR resistance (Strickler, Zhang et al. 2015). Other genomic alterations, including KRAS, NRAS, BRAF and EGFR somatic mutations may emerge under the selective pressure of anti-EGFR therapy (Diaz, Williams et al. 2012, Morelli, Overman et al. 2013, Morelli, Overman et al. 2014, Arena, Bellosillo et al. 2015). Additionally, cfDNA profiling often reveals concurrent gene mutations and copy number alterations. In a case series of 56 patients with RAS WT/ MET non-amplified tumors treated with anti-EGFR therapy, 14% of patients developed MET amplification upon progression (Morelli, Overman et al. 2013). Of these patients with acquired MET amplification, half also had concurrent RAS mutations (Morelli, Overman et al. 2014). These results have been reproduced in an ongoing clinical trial of cabozantinib plus panitumumab (NCT02008383). Among the first 26 patients with EGFR-refractory metastatic CRC receiving cfDNA profiling, 5 patients (19%) had MET amplified tumors (Strickler, Zhang et al. 2015). Concurrent BRAF and KRAS somatic mutations were detected in 2 out of 5 (40%) of these patients. These results illustrate the genomic complexity of acquired resistance.

Approximately 30-40% of patients with EGFR-refractory metastatic CRC have an "actionable" molecular alteration. These actionable alterations include, but are not limited to *MET* amplification (10-15%), *EGFR* somatic mutations (10%), and *ERBB2* amplification or somatic mutations (7%). Additionally, patients with metastatic CRC may have other actionable alterations, including *FGFR* amplifications or translocations (5%), *RET* fusions (1%), and *TRK* fusion (<1%). This protocol will utilize blood-based genomic profiling to identify and treat actionable genomic alterations.

2.0 Goals

- 2.1 Primary
 - 2.11 To perform blood-based genomic profiling on patients with treatment refractory metastatic CRC to facilitate accrual to molecularly assigned therapies.
 - 2.12 To facilitate clinically annotated genomic analyses.

3.0 Patient Eligibility

- 3.1 Inclusion Criteria
 - 3.11 Age \geq 18 years.

- 3.12 Histological confirmation of adenocarcinoma of the colon or rectum that is metastatic and/ or unresectable.
- 3.13 Progression, intolerance, or contraindication to a fluoropyrimidine (e.g., 5-fluorouracil or capecitabine), oxaliplatin, irinotecan, an anti-VEGF monoclonal antibody (bevacizumab, ziv-aflibercept, or ramucirumab), and an anti-PD-1 monoclonal antibody (nivolumab or pembrolizumab) if tumor has deficient mismatch repair proteins (dMMR) or is microsatellite instability-high (MSI-H).
- 3.14 For patients with *KRAS* and *NRAS* wild-type tumors, progression, intolerance, or contraindication to an anti-EGFR monoclonal antibody (cetuximab or panitumumab). Note: If tissue is known to be positive for HER2 expression (IHC 3+) or the tumor has *ERBB2* (HER2) amplification detected by a CLIA-certified assay, prior treatment with anti-EGFR therapy is not required.
- 3.15 At least one site of disease that is measurable by RECIST criteria (version 1.1) that has not been previously irradiated; if the patient has had previous radiation to the target lesion(s), there must be evidence of progression since the radiation (see section 11).
- 3.16 Life expectancy \geq 3 months per estimation of investigator.
- 3.17 ECOG Performance Status (PS) 0, 1, or 2 (Form is available on the ACCRU web site
- 3.18 Capable of understanding and complying with the protocol requirements and has signed the informed consent document.
- 3.19 Satisfy at least one of the following two conditions:
 - Willing and able to provide blood sample for screening purposes (See Section 14.0).
 - Guardant360 testing completed ≤ 60 days prior to registration is available for COLOMATE steering committee to review.

3.2 Exclusion Criteria

- 3.21 Evidence within the last 3 years of another malignancy which required systemic treatment. EXCEPTIONS: Non-melanotic skin cancer, carcinoma-in-situ of the cervix, or localized prostate cancer with a current PSA of < 1.0mg/dL on 2 successive evaluations, at least 90 days apart, with the most recent evaluation no more than 4 weeks prior to registration.
- 3.22 Unable or unwilling to abide by the study protocol or cooperate fully with the investigator or designee.
- 3.23 History of solid organ transplantation.
- 3.24 Pregnant or planning to become pregnant within the next 12 months.

4.0 Test Schedule

	Active Monitoring		
Tests and Procedures	≤60 days prior	Registration/	30 Days after
	to registration	Baseline	Registration (±3 days)
Informed Consent	X		
Demographics	X		
Medical and Cancer History	X		
Physical Examination	X		
Height	X		
Weight	X		
Vital Signs	X		
ECOG Performance Status	X		
Cell-Free DNA Analysis ^{1,R}		X^2	
COLOMATE			
Companion Trial		X^3	
Recommendation			
Form			4
Nurse/CRA phone			X^4
contact			

1	Kits are required for this collection. Please reference Section 14 for instructions. Sites will
	access results through the Guardant Health portal:
	will be notified by Guardant Health via email when results are available in the portal.
	Following receipt of results, sites must email the de-identified results to
	See detailed instructions on the ACCRU website under
	Manuals and Forms

2 If the patient has received Guardant360 testing ≤ 60 days of registration, these test results will be accepted for study and cell-free DNA analysis will not be repeated (no blood drawn at baseline). To receive test results, if not already available, the patient will fill out the Authorization to Use and Disclose Health Information form found on the ACCRU website under Manuals and Forms. Guardant will send the results to the site contacts they list on the authorization form. Sites will then email the de-identified results to

See detailed instructions on the ACCRU website under Manuals and Forms.

- Complete top portion of COLOMATE Companion Trial Recommendation Form and email to The COLOMATE steering committee will complete the form and send to treating physician and CRA within 5 business days of receipt of Guardant360 results. The treating physician/CRA will provide this form to the appropriate companion trial study team.
- 4 Nurse/CRA to call patient 30 days after the date of registration to collect status of registration to companion trial needed to complete On-Study Form.
- R Research funded (see Section 19)

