6.1 Initial Registration

Friday).

To register a patient, access the ACCRU web page at
go to the Remote Application
section, click on "Registration" and enter the registration/randomization
application. The registration application is available 24 hours a day, 7 days a
week. Back up and/or system support contact information is available on the
Web site. If unable to access the Web site, call the Academic and Community
Cancer Research United (ACCRU) Registration Office at
between the hours of 8 a.m. and 4:30 p.m. Central Time (Monday through

Instructions for the registration application are available on the above web page under the Remote Application section, "Remote Application Training."

Prior to initiation of protocol study intervention, this process must be completed in its entirety and an ACCRU subject ID number must be available as noted in the instructions. It is the responsibility of the individual and institution registering the patient to confirm the process has been successfully completed prior to release of the study agent. Patient registration via the registration/randomization application can be confirmed in any of the following ways:

- Contact the ACCRU Registration Office III If the patient was fully registered, the Registration Office staff can access the information from the centralized database and confirm the registration.
- Refer to "Remote Registration, Installation & Entry Instructions" under "Training Material Manuals."

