6.2 Subsequent Registrations

6.21 To register a patient, fax () a completed eligibility checklist to the Academic and Community Cancer Research United (ACCRU) Registration Office between 8 a.m. and 4:30 p.m. central time Monday through Friday.

NOTE: Patients have the option to register on COLOMATE for a maximum of 3 times or at the discretion of the Study Chair. Patients must reconsent and meet eligibility criteria in section 3 and will receive a new patient ID.

- 6.3 At the time of registration, the following will be recorded:
 - Patient has given permission to share his/her data for future research to learn about, prevent, or treat cancer or other health problems (for example: diabetes, Alzheimer's disease, or heart disease).
 - Patient has given permission for ACCRU to share his/her data to outside researchers.
- 6.4 Documentation of IRB approval must be on file with ACCRU before an

investigator may register any patients. Approvals should be uploaded through the online ACCRU Regulatory Management System (ARMS).

In addition to submitting initial IRB approval documents, ongoing IRB approval documentation must be on file with ACCRU no less than annually. Approvals should be uploaded through the online ACCRU Regulatory Management System (ARMS). If the necessary documentation is not submitted in advance of attempting patient registration, the registration will not be accepted and the patient may not be enrolled in the protocol until the situation is resolved.

Submission of annual IRB approvals to ACCRU is required until the study is closed through your IRB*.

*Please note, if the study site IRB determines that the study meets requirements for a minimal risk study, per the Revised Common Rule, any study approved after January 21, 2019, is not required to provide continuing/annual reviews.

- 6.5 Prior to accepting the registration, the registration application will verify the following:
 - IRB approval at the registering institution
 - Patient eligibility
 - Existence of a signed consent form
 - Existence of a signed authorization for use and disclosure of protected health information
- 6.6 Study-specific activities cannot begin prior to registration and must begin ≤30 days after registration.
 - NOTE: Guardant360 testing completed ≤ 60 days prior to registration will be accepted.
- 6.7 Pretreatment tests/procedures (see Section 4) must be completed within the guidelines specified on the test schedule.

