7.7 Evaluation procedures

7.71 Each patient will be contacted by telephone 30 days (\pm 3 days) after registration to document the patient's status of registration to a companion study. This

information is needed to complete the On-Study form.

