16.2 Primary Endpoints

There are two primary endpoints for this trial:

- The first primary endpoint is "actionable genomic profile" defined as a patient who
 received a trial recommendation per the COLOMATE companion trial
 recommendation form.
- The second primary endpoint is "companion trial enrollment" defined as a patient who has an actionable genomic profile that enrolls in their recommended companion trial.

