16.5 Analysis Plan

16.51 Primary Endpoints

For the analysis of the first primary endpoint, the proportion of patients who
have an actionable genomic profile will be calculated. This is defined as the
total number of eligible patients who have an actionable genomic profile
divided by the total number of eligible patients whose genomic profile is
available for COLOMATE steering committee review.

A patient may come back to ACCRU-GI-1611 for subsequent screening (see sections 7.5, 7.5, and 7.6); therefore, a patient can contribute information to the first primary endpoint more than once.

- Our goal is to have at least 20% of patients have actionable genomic profile. The endpoint will be presented as a point estimate along with a 95% confidence interval (by Wald asymptotic confidence limit).
- For the analysis of the second primary endpoint, the proportion of patients that enroll in the companion trial recommended by the COLOMATE committee will be calculated. This is defined as the total number of eligible patients that enroll in the recommended companion trial divided by the total number of eligible patients who have an actionable genomic profile.

A patient may come back to ACCRU-GI-1611 for subsequent screening (see sections 7.4, 7.5, and 7.6); therefore a patient can contribute information to

the second primary endpoint more than once.

• Our goal is to enroll at least 75% of patients who have an actionable genomic profile. The endpoint will be presented as a point estimate along with a 95% confidence interval (by Wald asymptotic confidence limit).

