18.0 Records and Data Collection Procedures

18.1 Submission Timetable

Initial Material(s)

initial Waterial(s)	
CRF	Active-Monitoring Phase (Compliance with Test Schedule Section 4)
Institutional Contacts	30 days (±3 days) after registration
On-Study	
Supporting Documentation: Baseline ¹	
Specimen Submission: Blood - Baseline	
(see Section 14) ²	
Patient Status: Baseline	

- 1. Pathology report confirming adenocarcinoma, all available tumor molecular testing reports (KRAS, NRAS, BRAF, MSI-H, etc.), Guardant360 test results, and COLOMATE Companion Trial Recommendation Form.
- 2. Submit if Guardant360 (cfDNA) test is done after registration to COLOMATE.

Test Schedule Material(s)

1 est Schedule Material(s)		
	Active-Monitoring Phase (Compliance with Test Schedule Section 4)	
CRF		
	At Receipt of	At any
	Guardant360 Testing	occurrence
Consent Withdrawal ¹		X
Consent Withdrawal: Specimen Only ¹		X

CRF	Active-Monitor (Compliance with Test S	
	At Receipt of	At any
	Guardant360 Testing	occurrence
Deviation Form ¹		X
DNA Testing Dates (Internal Use Only-		X
ACCRU Office)		

^{1.} Submit only if applicable.

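### Companion-trial enrolment is a primary endpoint with no time limit, but the only status check described is one call at day 30±3, which can come before the recommendation or the enrolment

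*Combined protocol and SAP*

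**What the plan says.** Section 16.2 defines the second primary endpoint as a patient who "has an actionable genomic profile that enrolls in their recommended companion trial". Section 16.51 makes this a proportion, the "total number of eligible patients that enroll in the recommended companion trial divided by the total number of eligible patients" with an actionable profile, reported with a Wald 95% interval. It adds a target: "Our goal is to enroll at least 75% of patients who have an actionable genomic profile". Neither section gives a time limit, a data cut-off or a data source.

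The collection of enrolment status is described elsewhere. Section 4, footnote 4, has: "Nurse/CRA to call patient 30 days after the date of registration to collect status of registration to companion trial", for completing the On-Study form. Section 7.71 repeats it: "Each patient will be contacted by telephone 30 days", give or take 3 days, after registration. Section 18.1 lists the On-Study form with the initial material, at the same time point.

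Three timing rules bear on whether the call is late enough. Section 6.6 requires study-specific activities to begin no later than 30 days after registration. Section 4 and Section 7.31 give the steering committee 5 business days from receipt of the assay results to return its recommendation. Assay turnaround is not stated.

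**The concern.** The endpoint as defined counts enrolment whenever it happens. The collection as described sees only what has happened by about day 30. The denominator depends on the recommendation form, which is not tied to the call. A patient who is recommended, whether before or after the call, and who enrols after it is therefore in the denominator but missing from the numerator.

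The error runs in one direction and does not shrink with more patients. What is at stake is how a primary result is read against its 75% goal: enrolment by about day 30 and enrolment at any time are different quantities, and the goal could be missed on the first and met on the second.

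**Working it through.** **1. Is any other source described?** Beyond the initial material, 18.1 lists two consent-withdrawal forms (one of them "Consent Withdrawal: Specimen Only"), a deviation form and DNA testing dates. None is described as recording enrolment. Section 6.1 says that "Registration Office staff can access the information from the centralized database and confirm the registration", but this concerns checking that a patient was registered and is not linked to the endpoint. Section 7.31 sends the recommendation form to the companion trial's team, and no return of enrolment data is described.

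**2. Can recommendation follow the call?** The call falls between day 27 and day 33. Assay turnaround is assumed to be 7 to 14 calendar days, and 5 business days are taken as 7 calendar days. Latest recommendation day = draw day + turnaround + 7.

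| Draw day | Recommendation by day | Days left before a day-30 call |
|---|---|---|
| 0 | 14 to 21 | 16 to 9 |
| 14 | 28 to 35 | 2 to −5 |
| 30 (allowed by 6.6) | 44 to 51 | −14 to −21 |

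For a day-30 draw, even a committee that answers at once, after the shortest assumed turnaround, gives 30 + 7 = day 37, after the last permitted call on day 33. For a day-0 draw, companion-trial consent and eligibility checks must fit into 9 to 16 days if the committee uses its full allowance.

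**3. Reproducing the plan's precision figures.** Half-width = 1.96 × √(p(1−p)/n), with n = 200 (40% of 500, Section 16.4). For p = 5, 10, 15, 20, 25 and 30% this gives 3.02, 4.16, 4.95, 5.54, 6.00 and 6.35 points, matching all six tabulated rows. The table has no 75% row. Because p(1−p) is symmetric, the half-width at 75% equals that at 25%: (31.00 − 19.00)/2 = 6.00 points.

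**4. Effect of late enrolments.** Let f be the share of enrolments that happen after the call. The documents give no basis for f, so 5, 10 and 20% are assumptions. Recorded rate = p(1−f); bias = p × f; n = 200.

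| True p | f | Recorded | Wald 95% CI | Bias (points) | Half-width at p (points) |
|---|---|---|---|---|---|
| 75% | 5% | 71.25% | 65.0 to 77.5 | 3.75 | 6.00 |
| 75% | 10% | 67.5% | 61.0 to 74.0 | 7.5 | 6.00 |
| 75% | 20% | 60.0% | 53.2 to 66.8 | 15.0 | 6.00 |
| 30% | 10% | 27.0% | 20.8 to 33.2 | 3.0 | 6.35 |
| 30% | 20% | 24.0% | 18.1 to 29.9 | 6.0 | 6.35 |
| 20% | 20% | 16.0% | 10.9 to 21.1 | 4.0 | 5.54 |

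Bias exceeds the half-width when f is above half-width/p. At the goal this is 6.00/75 = 8%. Across the tabulated 5 to 30% range the threshold falls from 3.02/5 = 60% to 6.35/30 = 21%, so f up to 20% stays within sampling error throughout that range.

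**The case against.** A source and a time point can be inferred. Protocol and statistical section are one document, and Section 4, 7.71 and 18.1 together name a call, a form and a date for exactly this status. It would go too far to say that the endpoint has no source, and this objection stands. It does not resolve the mismatch, because Section 16 neither adopts day 30 as the limit nor says how later enrolments count.

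Silence is also weak evidence that no later update exists. Form contents are not in the documents, further instructions sit in manuals that are not reproduced, and the 18.1 tables are damaged in extraction. A reader might infer that late enrolments will be lost. The documents support only that no means of capturing them is described.

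The timeline in step 2 includes an extreme case. The test schedule places the draw at registration/baseline, and patients with an acceptable prior Guardant360 result need no draw. Many recommendations may come well before day 30. That limits how often the problem arises, but 6.6 permits it, and an early recommendation can still be followed by a late enrolment.

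Finally, f is purely assumed, 16.3 says the analysis is descriptive, and 75% is a goal with no decision attached. All of that stands and bears on severity.

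**Conclusion.** The concern holds in this form: the endpoint is defined without a time limit, the only described status collection is one call at day 30±3, and the plan's own timing rules allow recommendation and enrolment after that call. If the analysis relies on the call, and the denominator is as 16.51 defines it, omitted late enrolments can only lower the recorded proportion.

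The size is unknown. At a true 75% with 200 recommended patients, bias passes sampling error once more than 8% of enrolments are late. At an assumed 10% the interval excludes the goal, while at 5% it still covers it. At the 5 to 30% rates the plan tabulates, the effect stays inside the half-width for late shares up to 20%.

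The figures should not be read as showing that the reported rate will be biased by any given amount, or that the goal will be missed; the documents contain no time-to-enrolment data. No hypothesis test or error rate is affected. Severity is minor to moderate. How enrolments are credited when a patient re-registers is a separate matter and forms no part of this point.

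**What to change.** In 16.2 and 16.51, state that enrolment is determined from companion-trial registration dates, taken from companion-trial records or from one later status check for each recommended patient. Count enrolments up to a stated cut-off, timed from the recommendation rather than from registration, so that a late draw does not shorten a patient's opportunity to be counted. The documents give no basis for choosing its length; the sponsor should set it. If such a source is already in use, a sentence naming it and the cut-off is enough.

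If no later check is made, relabel the endpoint as enrolment known by day 30±3 after registration, and read the 75% goal on that basis.

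The cost is a minor amendment, one lookup or contact per recommended patient (0.40 × 500 = about 200), and slightly later final data. The relabelling needs no extra data.
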